4.2.3. Methods of Pooling Data

Not applicable to the present study.

4.2.4. Adjustments for Covariates

No formal statistical analysis that adjusts for possible covariate effects is planned.

4.2.5. Multiple Comparisons/Multiplicity

Not applicable.

4.2.6. Subpopulations

Not applicable to the present study.

4.2.7. Discontinuations and Loss to Follow-up

Each treated patient from this study receives study medication as two single IA injections. Therefore, discontinuation from treatment is not applicable. Whether or not patients may receive the entire content of study drug injection will be considered in the study drug exposure analyses.

Each patient may only discontinue from the study for further assessments and study visits. Data collected from discontinued patients will be included in the CSR. Patients who discontinue from the study may be replaced at the discretion of the sponsor.

4.2.8. Missing, Unused, and Spurious Data

Missing values will not be imputed and data will be analyzed “as observed”.

4.2.9. Visit Windows

Visit windows will be calculated based on the schedule of assessments.

All endpoints will be summarized and presented according to the nominal visit (and hour, if applicable) as recorded on the Case Report Form (CRF).

4.2.10. Baseline definitions

For all endpoints, for exposed patients, baseline is the Baseline/Day 1 assessment prior to study drug administration date and time, in the first knee. If baseline result is missing, the first non-missing result prior to study drug administration may be used from the Screening period. For randomized and not exposed patients the latest assessment during the screening period will be used.

4.3. Interim Analyses

An interim analysis is not planned for this study.

4.4. Patient Disposition

All patients who are enrolled will be accounted for in this study.

Patient disposition will be tabulated and include the number randomized, treated and completed; the number in each patient population for analysis; and the number who discontinued prior to completing the study and reason(s) for discontinuation.

Summary data will be presented by treatment arm and overall.

A by-patient data listing of study completion information including the reason for early study discontinuation, if applicable, will be presented.

A listing of patients by analysis population will also be provided, including reason for exclusion from an analysis population.

4.5. Protocol Deviations

All protocol deviations will be presented in a data listing.

4.6. Demographic and Baseline Characteristics

Demographic and baseline characteristics will be summarized on the safety population and will be presented by treatment group.

No formal statistical comparisons will be performed.

All collected demographic, baseline characteristic, bilateral knee assessment and medical history data will be provided on the safety population.

All collected demographic, baseline characteristic, and medical history data will be provided in data listings.

4.6.1. Demographic characteristics

The following baseline parameters will be described:

- Age (year) at consent - Age will be calculated as the years between date of birth and date of informed consent, and will be rounded down to the nearest year.
- Weight (kg);
- Height (cm);
- Gender (Male/Female);
- Body mass index (BMI) (kg/m²);
- BMI category:
 - Underweight: <18.0 kg/m²
 - Normal: 18.0 to <25.0 kg/m²
 - Overweight: 25.0 to <30.0 kg/m²
 - Obesity Class I: 30.0 to <35.0 kg/m²
 - Obesity Class II: 35.0 to <40.0 kg/m²
 - Obesity Class III: >=40.0 kg/m²
- Ethnicity (Hispanic or Latino / Not Hispanic or Latino);
- Race (White, Asian / Black or African American / American Indian or Alaska Native / Native Hawaiian or Other Pacific Islander);
- Country.

Age, height, weight, and body mass index (BMI) will be summarized using descriptive statistics (number of patients, mean, standard deviation, median, minimum, and maximum). The number and percentage of patients in each gender, ethnicity, race and BMI category will also be presented.

4.6.2. Osteoarthritis (OA) Medical History

General OA and knee OA medical history data as collected on the CRF will also be tabulated for the Safety Population.

For each knee, time from primary diagnosis of OA in the knee to Day 1 of the study in days (first dose date – date of diagnosis + 1), will be computed and presented descriptively. If only month and year of initial diagnosis is available, day will be imputed as 1 for calculations. If month and day are missing, the time from primary diagnosis will be computed as year of first dose minus year of diagnosis. If year is missing, time from diagnosis will not be computed.

Knee OA history data will be summarized by knee injected (first injection and second injection separately).

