7.9.2. Review of Eligibility, Medical History, Prior Treatment and Medications

Eligibility criteria (inclusion and exclusion criteria), medical history (including OA history), and prior treatment and medications are reviewed during screening and again pre-dosing on Day 1.

OA medical history includes ACR diagnosis details, OA diagnosis date (if available), number of days with pain in both knees in the last month, and previous IA steroid or hyaluronic injections.

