2. STUDY DESIGN

2.1. Synopsis of Study Design

This randomized, parallel group study will be conducted in male and female patients \geq 40 years of age with bilateral knee OA.

Approximately 24 patients will be randomized to one of two treatment groups (1:1) and treated with two single IA injections of either:

1. extended-release FX006 64 mg total dose (approximately 12 patients) or
2. immediate-release TAcS 80 mg total dose (approximately 12 patients).

Each patient will be evaluated for a total of 6 weeks following the two IA injections. Following screening, PK and safety will be evaluated at 6 out-patient visits scheduled on Study Days 1 [calendar day of injection], 2, 8, 15, 29, and 43.

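### SAP 4.6.2 defines time since OA diagnosis in days, but its rule for year-only dates returns whole years with no conversion

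*SAP*

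**What the plan says.** SAP 4.6.2 sets up one variable, to be derived knee by knee and presented descriptively: "time from primary diagnosis of OA in the knee to Day 1 of the study in days (first dose date – date of diagnosis + 1"). Three rules for incomplete diagnosis dates follow.

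- Day missing: "If only month and year of initial diagnosis is available, day will be imputed as 1 for calculations".
- Month and day missing: "If month and day are missing, the time from primary diagnosis will be computed as year of first dose minus year of diagnosis".
- Year missing: "If year is missing, time from diagnosis will not be computed".

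The same section adds: "Knee OA history data will be summarized by knee injected (first injection and second injection separately"). SAP 7.1 lists Table 14.1.3 for OA history and bilateral knee characteristics in the Safety Population. Protocol 7.9.2 collects the "OA diagnosis date (if available"), so incomplete or absent dates are foreseen.

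**The concern.** The first rule supplies a missing day and leaves the main formula in place, so its result stays in days. The second replaces the formula with a subtraction of calendar years. No multiplier, second variable or separate table row goes with it, and nothing elsewhere in the SAP or protocol supplies one. This is therefore a stated rule that gives a value in the wrong unit. It is not merely a detail left open.

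At stake is the accuracy of disease duration by arm in the baseline table. The arms are small ("extended-release FX006 64 mg total dose (approximately 12 patients") in one, and about 12 in the other), so a few affected records can shift the mean and SD visibly. A chance difference between arms in the number of year-only dates could make duration look unbalanced, or hide a real difference. Because the variable is computed per knee, a patient with year-only dates for both knees is wrong in both the first-injection and the second-injection summaries.

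**Working it through.** The documents give no figure for this variable, so there is none to reproduce. The check applies the SAP rules to one example.

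**Inputs**

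- Main formula, unit and incomplete-date rules: SAP 4.6.2.
- Arm size, about 12: SAP 2.1.
- Assumed first dose date, 15 March 2018, and true diagnosis date, 15 March 2008. Both are illustrative.
- Assumed number of year-only records per arm: 0 to 6 of 12.

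**One patient with a 10-year history**

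| Information available | Calculation | Value entered |
|---|---|---|
| Full date | 15 Mar 2018 − 15 Mar 2008 + 1 = 3,652 + 1 | 3,653 |
| Month and year | 15 Mar 2018 − 1 Mar 2008 + 1 = 3,666 + 1 | 3,667 |
| Year only | 2018 − 2008 | 10 |

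The month-and-year rule is 14 days off. The year-only rule is too small by a factor of 3,653 / 10 = 365.3. A diagnosis known only as 2008 lies between 3,362 days (31 December) and 3,727 days (1 January) before dosing, counted by the SAP formula, so 10 is far outside any possible value.

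**Boundary case.** For a diagnosis in the dosing year, the year-only rule gives 2018 − 2018 = 0. The days formula gives at least 1 for any diagnosis on or before Day 1. Eligibility does not exclude this case: inclusion criterion 3 (Protocol 7.4.2) requires six months of symptoms, not six months since diagnosis.

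**An arm of 12, all with 10-year histories, k of them year-only**

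Mean = 3,653 − k × (3,653 − 10) / 12 = 3,653 − 303.6k.

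Sample SD = 3,643 × √[k(12 − k) / (12 × 11)].

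| k | Mean | Change in mean | Median | Minimum | SD |
|---|---|---|---|---|---|
| 0 | 3,653 | none | 3,653 | 3,653 | 0 |
| 1 | 3,349 | −8% | 3,653 | 10 | 1,052 |
| 3 | 2,742 | −25% | 3,653 | 10 | 1,648 |
| 6 | 1,832 | −50% | 1,832 | 10 | 1,902 |

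The true SD of 0 follows from giving everyone the same history. Real durations would vary, so the SD column shows the direction and rough scale of the inflation and is not a forecast. The flat median up to k = 3 has the same origin: with varied durations, misplaced records would shift the median by ranks, still much less than they shift the mean.

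**Candidate repairs on the same patient**

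- 1 January 2008 imputed: 3,727 days, 74 too many. The largest possible error is 3,727 − 3,362 = 365 days.
- 1 July 2008 imputed: 3,652 − 108 + 1 = 3,545 days. The largest possible error is 183 days (3,545 − 3,362).
- For a 2018 diagnosis, an uncapped 1 July gives −108 + 1 = −107 days, while 1 January gives 73 + 1 = 74.

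**The case against.** **Pooling is not stated.** A reader might infer that the SAP directs year-only values to be pooled with day values and labelled as days. It does not say so. It says the time is computed and presented descriptively, and SAP 7.1 gives only a table title. A programmer might convert the value or give it a separate row. This stands as far as it goes: the outcome is what literal application produces. It does not rescue the rule, because a silent conversion would be an undocumented departure from the plan.

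**The frequency is unknown.** It is tempting to argue that diagnosis dates in long-standing OA are usually known only to the year. The documents contain nothing to that effect. Protocol 7.9.2 shows only that dates may be unavailable, and the number of year-only dates could be zero. This stands, which is why the size is given over an assumed range.

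**The variable drives nothing.** SAP 4.6 rules out formal comparison of baseline data, SAP 4.2.4 plans no covariate adjustment, and SAP 4.2.6 has no subpopulations. The linear model in SAP 4.8.4 has treatment as its only fixed effect, and the bioequivalence model in SAP 4.8.5 has treatment, site and patient. Protocol 9.2 allows optional sensitivity analyses for baseline imbalance, but it names no variable and the SAP specifies none. By-patient listings (SAP 4.6; Listing 16.2.4.3 in SAP 7.3) would also let a reader trace an odd value. All of this stands and limits the importance of the point. None of it makes the formula right.

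**Conclusion.** The point holds as a unit error in a stated rule. Applied literally, each year-only record is understated about 365-fold in the 10-year example. Over the assumed range of 0 to 6 such records in an arm of 12 with uniform 10-year histories, the mean falls by 0 to about 50%. One record is enough to give a minimum of 10 and inflate the SD. The median is robust until about half the records are affected.

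A reader might go further and infer that the error threatens the exposure comparison or the safety conclusions. The documents do not support that: in the planned analyses the variable appears only as a descriptive baseline characteristic. Any apparent imbalance would be confined to the time-since-diagnosis summaries in the OA history table. This is a minor correction, worth making before the tables are programmed.

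**What to change.** Amend the year-only rule in SAP 4.6.2 in one of two ways.

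- **Keep days.** Impute a month and day, then apply the existing formula. 1 January is the counterpart of the day-1 rule, since both take the start of the known period, and it cannot fall after the first dose unless the diagnosis year does. A mid-year date roughly halves the largest error, but it needs a cap at the first dose date to avoid zero or negative durations when diagnosis and dosing share a calendar year.
- **Use years throughout.** Compute and report the variable in years for every patient. This means rewriting the definition as well as the year-only sentence.

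The first option is a one-sentence change. Its cost is an imputation error of up to about a year per year-only record (at most 365 days with 1 January and 183 with 1 July in the example). It also extends the exception that SAP 4.6.2 already makes to the general no-imputation rule in SAP 4.2.8. Flagging year-only records in the listing would let readers see which values are imputed.

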4.6.3. Prior medication

All prior medications will be presented in the concomitant medication data listing with a flag identifying which medications are prior medications (refer to Section 4.9.4 for details on defining prior and concomitant medications).

4.7. Pharmacodynamics Evaluation

The actual value and change from baseline (Day 1 or Screening if Day 1 is missing) will be summarized for serum cortisol levels by actual treatment arm. In the event of repeat values, the last non-missing value per study day/time will be used.

All serum cortisol data will be provided in tables and listings. Results falling outside of the expected collection time of 7:00am to 9:00 am will be flagged”

4.8. Study Drug Exposure and Pharmacokinetics Evaluation

4.8.1. Study Drug Exposure

Details of study drug administration will be tabulated and presented by actual treatment arm and knee injected (first injection and second injection separately) for the Safety Population. Specifically, the position of the knee during injection, the approach during injection, the numbing agent to be used, whether or not the entire contents of the syringe was injected, and whether a 21 gauge or larger needle was used will be presented.

The time between the first knee IA injection and second knee IA injection will be included in listings.

All dosing data will be presented in a data listing.

4.8.2. Plasma drug concentration analysis

Tabular summaries of mean TA plasma concentrations, by treatment for each nominal sampling time will be presented for the PK population.

Visit date and times are calculated relative to the Baseline/Day 1 visit. The reference time point is Day 1 time of 1st study drug administration in the first knee (Time 0). Of note, the pre-dose sample is only relevant if a quantifiable concentration of TA is present.

All data collected will be summarized and presented in individual plots. However, all data will be presented in data listings with those results falling outside of the visit window flagged. Both nominal (planned) and actual sampling time will be presented.

Descriptive statistics (n, mean, SD, geometric mean, log-scale SD, 95% CI, median, minimum, maximum) will be calculated by time point for plasma drug concentration levels. Frequencies of patients with values identified as BLOQ will be presented by time point.

4.8.3. Handling of Concentration Data below the Limit of Quantification (BLOQ)

The bioanalytical assay sensitivity for TA will be noted in the table and listings. Values assayed below these limits will be identified as BLOQ. Concentrations that are not detected will be identified as “Not Detected” and recorded as BLOQ.

For the PK analysis and individual concentration vs. time plots, a concentration that is BLOQ is assigned a value of zero if it occurs in a profile before the first measurable concentration. If a BLOQ value occurs after a measurable concentration in a profile and is followed by a value above the lower limit of quantification, then the BLOQ is treated as missing data. If a BLOQ value occurs at the end of the collection interval (after the last quantifiable concentration) it is set to zero. If two BLOQ values occur in succession after Cmax, the profile is deemed to have

terminated at the first BLOQ value and any subsequent concentrations are set to zero for PK calculations.

4.8.4. Pharmacokinetic analysis

PK analysis will be performed on the PK population. PK parameter estimates will be completed by the study pharmacokineticist and results provided for incorporation into study datasets.

PK parameters will be derived using model-independent methods (non-compartmental analysis (NCA)) as implemented in Phoenix 7, WinNonlin® (version 7) and will be based on TA plasma concentrations from patients in the PK Population. Mean concentration profiles will be computed for each treatment arm: FX006 64 mg and TAcS 80 mg.

Actual sampling times will be used for the estimation of the PK parameters if significant deviations from the nominal sampling time are noted in data review by the study pharmacokineticist. All descriptive summary tables and figures will be presented with the nominal (planned) sampling times.

All blood samples will be assayed for concentration levels of TA using a validated High Performance Liquid Chromatographic Method with Tandem Mass Spectrometry Detection method (LC/MS-MS), each matrix with a validated assay range in pg/mL. Bioanalytical methods for the assay of TA will be provided in a separate bioanalytical report that will include information on calibration standards for the assay.

Each PK parameter will be estimated for each patient with NCA methodology.

The PK endpoints to be computed on plasma TA concentration measurements will be either observed from those concentration measurements or estimated by WinNonlin® (version 7) using the trapezoidal rule for calculation of the AUC estimates to the last measureable concentration. Additional estimates of the half-life, clearance, residence time, volume of distribution and the extrapolated area for the $AUC_{0-\infty}$ and related parameters will be estimated using the slope estimate for the terminal elimination rate constant for each patient with WinNonlin® (version 7).

PK variables consist of PK parameters identified in Table 2.

Table 2 PK Parameters

PK Parameter	Description (Computation Method)
C_{max}	Peak exposure, Maximum plasma concentration observed.
t_{max}	Time from dosing to peak exposure, time to maximum plasma concentration observed.
C_{last}	Last quantifiable plasma concentration (last value observed above assay BLOQ)
t_{last}	Time of last quantifiable plasma concentration
λ_z	Terminal elimination rate constant (lambda_z)
$t_{1/2}$	Terminal half-life: Computed as $t_{1/2} = \frac{Ln(2)}{\lambda_z}$
$AUC_{(0-t)}$	Exposure: Area Under the Plasma Curve from time 0 to the last quantifiable concentration (t). Calculated using the linear trapezoidal rule.
$AUC_{(0-24)}$	Exposure: Area Under the Plasma Curve from time 0 to 24 hours post IA injection. Calculated using the linear trapezoidal rule
$AUC_{(0-\infty)}$	Exposure: Area Under the Plasma Curve from time 0 extrapolated to infinity. Calculated as follows: $AUC_{inf} = AUC_{(0-t)} + \frac{C_{last}}{\lambda_z}$ where C_{last} is the last quantifiable concentration.
CL	Total Body Clearance, computed as Dose/ $AUC_{(0-\infty)}$
MRT	Mean residence time extrapolated to infinity, computed as $AUMC_{(0-\infty)}/AUC_{(0-\infty)}$
Vz_F	Volume of Distribution, based on terminal phase, computed as : $\frac{Dose}{\lambda_z \cdot AUC_{(0-\infty)}}$

Descriptive summaries of the individual patient PK parameters and population summaries over all patients will be presented. Individual linear-linear and log-linear concentration profiles will be completed for each patient. Graphical display (plasma drug concentration curves) will be used to present geometric mean with 95% CIs for plasma drug concentrations (linear-linear and log-linear plots) for each treatment arm.

All PK parameters and data will be presented in a data listing. Results from the PK analysis will be included in the CSR. Along with the bioanalytical report from the assay laboratory, model output from the NCA analysis will be provided in a separate document.

A linear model will be used to compare the PK parameters from extended-release FX006 and immediate-release TAcS for each C_{max} , T_{max} , C_{last} , MRT, and AUC parameters. The model will include treatment as a single fixed effect. The least square mean difference (LSMD) between the two treatments will be explored to examine the magnitude of difference in exposure PK parameters between FX006 and TAcS. All p-values will be considered informative.

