5.2. Background

5.2.1. Investigational Medicinal Product: FX006

FX006 is an extended-release formulation of triamcinolone acetonide (TA) for IA administration. It is approved under the trade name ZILRETTA™ for the management of pain of osteoarthritis of the knee, however, injection in both knees has not been studied and is an investigational use. FX006 is intended to deliver TA to the synovial and peri-synovial tissues for a period of approximately 3 months depending on the dose administered. ([Bodick et al, 2013](#))

FX006 contains TA, United States Pharmacopeia (Ph. Eur/USP), formulated in 75:25 poly(lactic-co-glycolic acid) (PLGA) microspheres with a nominal drug load of 25% (w/w) and is provided as a sterile white to off-white powder for reconstitution. The drug product is reconstituted with diluent containing an isotonic, sterile aqueous solution of sodium chloride (NaCl; 0.9% w/w), carboxymethylcellulose sodium (CMC; 0.5% w/w) and polysorbate-80 (0.1% w/w) to form a suspension prior to IA injection.

Further details of the physiochemical properties of FX006 can be found in the Investigator's Brochure (IB).

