5.2.4. Systemic and Local PK in Patients with Osteoarthritis of the Knee

Overall, FX006 displayed a favorable plasma PK profile relative to TAcS.

PK observations resulted in a controlled and stable release of TA from PLGA microspheres into synovial tissues, where concentrations remained high relative to plasma concentrations for at least 12 weeks. TA was absorbed systemically, with a plateau in plasma TA concentrations occurring in the first 24 hours post-dose, and slow elimination from the systemic circulation observed in the weeks thereafter.

Relative to TAcS, FX006 32 mg produced substantially lower peak plasma and systemic exposure to TA. FX006 performed as expected, prolonging the residence of TA in the joint while minimizing systemic exposure to TA.

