2.5.2. Pharmacokinetic Variables

Blood samples (4 mL per sample) for TA drug concentration measurements will be obtained from all patients at the following nominal, or planned, times:

- On Day 1, within 1 hour prior to administration of study medication (Nominal Time -1),
- On Day 1, at Hours 1, 2, 3, 4, 5, 6, 8, 10, and 12 (\pm 10 minutes) after injection of the first knee,
- On Day 2, at 24 (\pm 2 hours) after injection of the first knee,
- On Days 8, 15, 29, and 43 (time as convenient during the scheduled visit).

These represent a total of 15 samples from each patient, each sample representing 4 mL of blood, for a maximum estimated total volume of 60 mL of blood collected from each patient for drug concentration measurement.

Procedures for sample collection, handling, storage and shipment will be described in the Laboratory Manual. Plasma TA concentrations will be measured using an established validated LC-MS/MS method.

PK parameter endpoints are described in section 4.8.4.

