4. STATISTICAL METHODS

4.1. Sample Size Justification

4.1.1. Sample Size Considerations

In this study, it is expected that the systemic exposure in plasma of TA from extended-release FX006 should not exceed that of the immediate-release TAcS formulation for the key parameters of C_{max} , $AUC_{(0-t)}$, and $AUC_{(0-inf)}$.

In a previous PK study with knee OA patients (FX006-2015-009) the ratio of the mean exposure parameters for FX006 32 mg (N=60) and TAcS 40 mg (N=18) for C_{max} was 0.10 with the upper limit of its 90% CI being 0.15 and for $AUC_{(0-inf)}$ was 0.52 with the upper limit of its 90% CI being 0.86. The pooled coefficients of variation for the parameters was between 0.53 (C_{max}) and 0.68 (AUC_{0-inf}).

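### Linear trapezoidal AUC across 6- to 14-day sampling gaps would bias the FX006/TAcS AUC ratio low, by about 5–12% if TAcS declines over days and FX006 over weeks

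*SAP*

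**What the plan says.** SAP section 4.8.4 describes "using the trapezoidal rule for calculation of the AUC estimates to the last measureable concentration". Table 2 in that section makes the rule explicit for AUC(0-t): "Area Under the Plasma Curve from time 0 to the last quantifiable concentration (t). Calculated using the linear trapezoidal rule". The same rule is given for AUC(0-24). AUC(0-inf) is AUC(0-t) plus Clast/λz, and CL, MRT and Vz_F are computed from AUC(0-inf). Neither document mentions a logarithmic rule for the declining phase or a sensitivity analysis of the integration rule.

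Sampling is dense up to 24 hours. After that, SAP section 2.5.2 plans samples only "On Days 8, 15, 29, and 43 (time as convenient during the scheduled visit").

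Protocol section 5.2.4 describes FX006 as showing "slow elimination from the systemic circulation observed in the weeks thereafter", and Protocol section 5.2.1 says it is intended to deliver drug "for a period of approximately 3 months depending on the dose administered". No half-life is given for either product, and no LLOQ.

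SAP section 4.1.1 expects that FX006 exposure "should not exceed that of the immediate-release TAcS formulation for the key parameters of" Cmax, AUC(0-t) and AUC(0-inf). SAP section 4.8.5 reports ratios with 90% confidence intervals for Cmax, AUC(0-24) and AUC(0-inf). In SAP section 4.8.4, "A linear model will be used to compare the PK parameters from extended-release FX006 and immediate-release TAcS for each" of several parameters, including AUC and MRT.

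**The concern.** A straight line between two points on an exponentially falling curve lies above the curve, so the linear rule overstates the area of each interval. The overstatement depends on the gap measured in half-lives. Two formulations sampled at the same times but falling at different rates therefore carry different errors, and these do not cancel in the ratio. If immediate-release TAcS falls over days and extended-release FX006 over weeks, the TAcS area is inflated more and the ratio is too low. That favours the expected finding.

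Comparing systemic exposure is a primary objective, and SAP section 1.2 says the results will serve regulatory filings and manuscripts. The error is systematic: more patients would not reduce it, and the confidence interval would not show it.

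A minor related point: SAP section 2.4 records the actual time of every sample, but section 4.8.4 uses actual times in the non-compartmental analysis only after a deviation judged significant, a term it does not define.

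**Working it through.** The documents state no figure for integration error, so there is none to reproduce.

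**Inputs from the documents**
- Sampling at 0, 1–6, 8, 10, 12, 24, 168, 336, 672 and 1008 h (SAP 2.5.2). The gaps after 24 h are 144, 168, 336 and 336 h.
- Earlier study: Cmax ratio 0.10 and AUC(0-inf) ratio 0.52 (SAP 4.1.1). With one-phase decline these imply an FX006 half-life about 0.52/0.10 = 5.2 times that of TAcS.
- CV: "The pooled coefficients of variation for the parameters was between 0.53" (Cmax) and 0.68 (AUC(0-inf)).

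**Assumptions**
- One-phase decline and a true AUC(0-inf) ratio of 0.52.
- TAcS half-life 3–7 days and FX006 2–5 weeks, paired so that the Cmax ratio is 0.10–0.12.
- LLOQ between TAcS Cmax/50 and Cmax/2000.

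**Step 1: error per interval.** Linear area / true area = (x/2)·coth(x/2), with x = ln 2 × gap / half-life.

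| Half-life | 144 h gap | 168 h gap | 336 h gap |
|---|---|---|---|
| 72 h | 1.155 | 1.209 | 1.750 |
| 168 h | 1.029 | 1.040 | 1.155 |
| 336 h | 1.007 | 1.010 | 1.040 |
| 840 h | 1.001 | 1.002 | 1.006 |

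**Step 2: one case by hand.** Ignore absorption and take every sample as quantifiable. The share of total area in an interval is exp(−kt₁) − exp(−kt₂), with k = ln 2 / half-life. Total excess is the sum of share × (factor − 1).
- TAcS, 72 h: 0.595×0.155 + 0.159×0.209 + 0.038×0.750 + 0.0015×0.750 = 0.155.
- FX006, 336 h: 0.245×0.007 + 0.207×0.010 + 0.250×0.040 + 0.125×0.040 = 0.019.
- Ratio: 0.52 × 1.019/1.155 = 0.459, about 12% low.

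**Step 3: full calculation**, with absorption, LLOQ and extrapolation, as linear AUC(0-inf) ratio against a true 0.52.

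| TAcS / FX006 half-life | Linear ratio |
|---|---|
| 72 / 336 h | 0.458–0.470 |
| 96 / 504 h | 0.471–0.488 |
| 120 / 600 h | 0.480–0.483 |
| 168 / 840 h | 0.492–0.496 |

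This is 5–12% low. Linear-up/log-down returns 0.520 throughout, because it is exact for one-phase decline. A second calculation, with different absorption rates, λz by regression and FX006 fixed at 5.2 times the TAcS half-life, gives −5.3% (TAcS 7 days) to −12.3% (3 days).

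The AUC(0-t) ratio is also 5–12% below its own true value; for 72/336 h at LLOQ Cmax/2000 it is 0.402 against 0.455. By arm, AUC(0-inf) is 5–16% too high for TAcS and 0.2–1.9% for FX006. With AUMC by the same rule, the MRT ratio is 7–21% too high.

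**Step 4: outside the main case**
- Same half-life ranges without the pairing: 0.45–0.50, or 3–13% low.
- TAcS half-life 2 days: about 16–20% low. At 10 days: about 2–3% low.
- Both half-lives 14 days or more: within 1.6%.
- TAcS half-life 1 day and unquantifiable by Day 8: +0.1% to +2%, because its AUC(0-t) then ends at 24 h.
- FX006 half-lives of 60–180 h, which fit Protocol 5.2.4 poorly: 0.32–0.41 if TAcS (18–36 h) is quantifiable at Day 8, and 0.53–0.61 if TAcS (12–24 h) is last quantifiable at 24 h.

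**Step 5: against sampling error.** SD(log) = √ln(1 + 0.68²) = 0.617. SE = 0.617 × √(2/12) = 0.252. The bias is ln(0.52/0.496)/0.252 = 0.19 to ln(0.52/0.458)/0.252 = 0.50 standard errors.

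**Step 6: timing point.** If late samples shift by up to 24 h and are analysed at nominal times, the SD of the per-patient AUC(0-inf) error is 2–4% for TAcS and 1–2% for FX006.

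**The case against.** **The size rests on assumed half-lives.** This stands. The range runs from negligible to well above 12%, and the sign can reverse if TAcS is unquantifiable by Day 8. The documents do constrain it, however. Cmax and AUC ratios of 0.10 and 0.52 fit poorly with similar half-lives: under one-phase decline, 336 h in both arms would give a Cmax ratio of 0.51. A TAcS half-life of 14 days or more would need roughly 10 weeks for FX006.

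**No conclusion changes.** This also stands. The ratio remains below 1.0, bioequivalence is not expected, p-values are only informative, and the shift is at most about half a standard error. These facts limit the severity but do not make the reported ratio accurate.

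**AUC(0-t) is not among the ratios listed with confidence intervals.** Correct. It is a named key parameter and enters the linear model, but AUC(0-inf) is the affected ratio that will be reported.

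**Log-down is only a partial remedy.** It cannot replace missing samples between 24 h and Day 8. In one two-phase TAcS example it moved the ratio from 0.414 to 0.472 against a true 0.52. In the paired cases, 12–44% of FX006 AUC(0-inf) is extrapolated, so λz matters too. Log-down can even do worse: with a 21-day FX006 plateau, linear gives 0.535 and log-down 0.564. That shape conflicts with Protocol 5.2.4, which places the plateau in the first 24 hours.

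**Comparability with earlier studies.** Protocol section 7.3.3 calls the design similar to theirs, and their integration rule is not stated. If the earlier 0.52 was itself a linear-rule figure from similar sampling, the underlying ratio would be about 0.55–0.59 (0.52²/0.496 to 0.52²/0.458). This is a reason to report the linear result as well.

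**Conclusion.** The concern holds. Applied to gaps of 6–14 days, the linear rule gives the two arms unequal errors. With TAcS falling over 3–7 days, FX006 over 2–5 weeks and one-phase decline, the AUC(0-inf) ratio is understated by about 5–12%: 0.46–0.50 in place of 0.52. Mechanism and sampling gaps come from the documents; the half-lives and LLOQ are assumptions. The direction follows when TAcS declines faster and is still quantifiable at Day 8 or later. Cmax and AUC(0-24) are essentially unaffected; the AUC(0-24) error is under 1%. This should be corrected because it concerns a key parameter and a reported ratio and the correction is cheap, although it would not overturn a result near 0.52. The actual-time point is minor.

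**What to change.** In SAP section 4.8.4 and Table 2, specify linear-up/log-down (linear while concentrations rise, logarithmic while they fall) for AUC(0-t), for the AUC(0-t) part of AUC(0-inf), and for the matching AUMC. Keep the linear rule as a named sensitivity analysis for comparison with earlier FX006 studies. AUC(0-24) needs no change. The zeros that SAP section 4.8.3 assigns after the last quantifiable sample do not interfere, because AUC(0-t) ends at that sample. State in the report that log-down reduces the error from having no samples between 24 h and Day 8 but does not remove it. Also use the recorded elapsed time for every sample in the non-compartmental analysis.

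Cost: one software setting, one additional run and two or three SAP sentences, with no new data or visits. The downside is two sets of AUC values to report.
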